18.1.3. Serious Adverse Events

Serious adverse events (SAEs) are those events recorded as “Serious” on the Adverse Events page of the (e)CRF. A summary of serious TEAEs by SOC and PT will be prepared.

18.1.4. Adverse Events Leading to Death

TEAEs leading to Death are those events which are recorded as “Fatal” for the Outcome field on the Adverse Events page of the (e)CRF. A summary of TEAEs leading to death by SOC and PT will be prepared.

18.2. Deaths

If any patients die during the study, the information will be presented in a summary table and a data listing using SAF population. If a patient died during Monotherapy, then the data will be summarized under Monotherapy, else the summary will be provided under Combination Therapy.

Document: \\eedc-vnasc01\Biosdata\Menarini\NebAml\ZZA67778\Biostatistics\Documentation\SAP\SAP_Menarini_MEIN21AmNe-Hyp001_Final_V1.0

Author: [name]

Version Number:

Final V1.0

Version Date:

11Nov2022

Template No.: CS_TP_BS016 Revision 7

Reference: CS_WI_BS005

Effective Date: 01Nov2021

18.3. Laboratory Evaluations

Results from the central laboratory will be included in the reporting of this study for Hematology, Serum Chemistry, Urine Pregnancy Test, and Coagulation. A list of laboratory assessments to be included in the outputs is included in protocol Section 8.2.3.

Presentations will use SI Units.

The following summaries will be provided for laboratory data:

- Actual and change from baseline by visit (for quantitative measurements) for Combination Therapy using SAF population.
- A by-patient listing of all laboratory data and pregnancy test data will be presented for both Monotherapy and Combination therapy using the SAF population.

18.4. ECG Evaluations

The following ECG parameters will be reported for this study:

- PR Interval (msec)
- QRS Interval (msec)
- RR Interval (msec)
- QT Interval (msec)
- QTcF Interval (msec) [derived]
- HR (bpm)
- Overall assessment of ECG (Investigator's judgment):
 - Normal
 - Abnormal, Not Clinically Significant (ANCS)
 - Abnormal, Clinically Significant (ACS)

The following summaries will be provided for ECG data:

- Actual and change from baseline by visit (for quantitative measurements).
- Shift from baseline of ECG Interpretation Results.
- ECG parameters recorded in eCRF form "12 Lead ECG", will be summarized using the SAF population for the Combination therapy. All ECG data will be listed for both Monotherapy and Combination Therapy using the SAF population.

Document: \\weedc-vnasc01\Biosdata\Menarini\NebAml\ZZA67778\Biostatistics\Documentation\SAP\SAP_Menarini_MEIN21AmNe-Hyp001_Final_V1.0

Author: [name]

Version Number:

Final V1.0

Version Date:

11Nov2022

Template No.: CS_TP_BS016 Revision 7

Reference: CS_WI_BS005

Effective Date: 01Nov2021

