
 
weeks.
 
To assess the antihypertensive efficacy of the extemporaneous combination of NEB 5 mg with AML 5 mg or AML 10 mg by evaluating the patients who achieve BP goal (sitting BP <130/80 mmHg) at Visit 2 (Week 0), at Visit 3 (Week 4), and at Visit 4 (Week 8).
 
	
 
Number and proportion of patients achieving the BP goal (sitting SBP/DBP <130/80 mmHg) at Visit 2 (Week 0), Visit 3 (Week 4) and Visit 4 (Week 8).
 
	The proportion of patients at target is a very important clinical indicator of therapeutic success.
• To assess the compliance to the treatment (percentage of actual doses taken versus doses to be taken) at Visit 2 (Week 0), at Visit 3 (Week 4), and at Visit 4 (Week 8).	doses taken/doses to be taken) at Visit 2 (Week 0), Visit 3 (Week	Monitoring compliance is extremely important to better evaluate the efficacy and tolerability of the extemporaneous combination.
• To evaluate the safety and tolerability of the monotherapies (NEB 5 mg and AML 5 mg) and of the extemporaneous combinations (NEB 5 mg and AML 5mg or AML 10 mg) after 8 weeks of treatment.	
 
Safety and tolerability of the monotherapies (NEB 5 mg and AML 5 mg) and of the extemporaneous combinations (NEB 5 mg and AML 5mg or AML 10 mg) will be measured by incidence, intensity (severity), seriousness of Adverse Events (AEs) during the study period, (screening, run-in period and assessment period), relationship to the study treatments, Adverse events of special interest, clinically significant abnormal change in vital signs, electrocardiogram (ECG) (only at Visit 1 and Visit 4), laboratory parameters (if applicable) at Visit
 
	Incidence of adverse drug reactions (ADRs), AEs, serious adverse events (SAEs), vital signs, physical examination, ECG needs to be studied to address safety and tolerability of the extemporaneous combination.

MENARINI	Corporate Medical Department		ent
	Protocol Template		
Identification Number	Version Number	State	Effective date
FORM-000050125	2.0, CURRENT	Effective	08 Jan, 2021

OBJECTIVES	ENDPOINTS	JUSTIFICATION FOR ENDPOINTS
	2 (Week 0), Visit 3 (Week 4), and Visit 4 (Week 8).	
Exploratory		

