### Withdrawal of patient from the study

The patient may withdraw from the study at any time without explanation, without losing the right to future medical care. The participation of the patient may, at any moment, be terminated by the Investigator, if considered appropriate.

A patient can be withdrawn during the study for any of the following reasons:

- Any AE, which required treatment and study termination for the patient according to the Investigator's judgment.
- Abnormal renal function or liver enzyme parameters as described in Section 8.2.3.
- Patient becomes pregnant during the study.
- Request of the patient (without giving any reason).
- Investigator deems it to be in the best interest of the patient to discontinue.
- Failure to adequately comply with the dosing, evaluations, or other requirements of the study.
- If the patient meets an exclusion criterion (newly developed or not previously recognized) that precludes further study participation.
- Use of any prohibited medication that in the opinion of the Investigator or Sponsor necessitates the patient being withdrawn.

The reason for the withdrawal of study treatment, or withdrawal from the study must be well documented in the source documents and in the eCRF page and should capture the date and the specific underlying reason for discontinuation of study treatment or patient discontinuation/withdrawal.

MENARINI	Corporate Medical Department		
	Р	Protocol Template	
Identification Number	Version Number	State	Effective date
FORM-000050125	2.0, CURRENT	Effective	08 Jan, 2021

*Study Code:* MEIN/21/AmNe-Hyp/001

Patients who discontinue from the study early will be asked, anyway, to complete all the assessments of Visit 4. Patients may discontinue the study treatment, but remain in the study for follow-up, especially for safety study endpoints (if applicable).

If a patient has been discontinued/withdrawn due to an AE, the Investigator must immediately notify the relevant pharmacovigilance contact (see Section 9.9) and should be followed-up until the AE is resolved or the Investigator deems further observations or examinations as no longer medically indicated.

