6.3. Retests, Unscheduled Visits and Early Termination Data

In general, for by-visit summaries, data recorded at the nominal visit will be presented. Unscheduled measurements will not be included in by-visit summaries. Listings will include scheduled, unscheduled, retest and early discontinuation data.

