APPENDIX 1. PROGRAMMING CONVENTIONS FOR OUTPUTS

IQVIA Output Conventions

Outputs will be presented according to the following:

[Global Bios > Processes > GBIOS Processes - Implementation Guidelines and Templates > General Guidelines and Templates > Output Conventions.](#)

Dates & Times

Depending on data available, dates and times will take the form yyyy-mm-ddThh:mm:ss.

Spelling Format

English US

Presentation of Treatment Groups

For outputs, treatment groups will be represented as follows and in the given order:

Therapy	Treatment Group	For Tables, Listings and Figures
Monotherapy	NEB 5mg	NEB 5mg
Monotherapy	AML 5mg	AML 5mg
Combination Therapy	NEB+AML (5mg)	NEB+AML (5mg)
Combination Therapy	NEB+AML (10mg)	NEB+AML (10mg)

Presentation of Visits

Visit 1 (Week -4)

Visit 2 (Week 0)

Visit 3 (Week 4)

Document: \\weedc-vnasc01\Biosdata\Menarini\NebAm\ZZA67778\Biostatistics\Documentation\SAP\SAP_Menarini_MEIN21AmNe-Hyp001_Final_V1.0

Author: [name]

Version Number:

Final V1.0

Version Date:

11Nov2022

Template No.: CS_TP_BS016 Revision 7

Reference: CS_WI_BS005

Effective Date: 01Nov2021

Visit 4 (Week 8)
Early Termination

For outputs, visits will be represented as follows and in that order:

Long Name (default)	Short Name
Screening (Visit 1)	Scr (V1)
Baseline (Week 0) or Visit 2 (Week 0)	BL(W0) or V2 (W0)
Visit 3 (Week 4)	V3 (W4)
Visit 4 (Week 8)	V4 (W8)
Early Termination	ET

Listings

All listings will be ordered by the following (unless otherwise indicated in the template):

- Treatment group (Monotherapy and Combination Therapy),
- Center-subject ID,
- Date (where applicable).

Document: \\weedc-vnasc01\Biosdata\Menarini\NebAm\ZZA67778\Biostatistics\Documentation\SAP\SAP_Menarini_MEIN21AmNe-Hyp001_Final_V1.0

Author: [name]

Version Number:

Final V1.0

Version Date:

11Nov2022

Template No.: CS_TP_BS016 Revision 7

Reference: CS_WI_BS005

Effective Date: 01Nov2021

Reference Code

- Paired t-test

```
ods trace on;  
proc ttest data=input_data h0=0;  
  paired VISITX*VISITY;  
  ods output TTests=test;  
run;  
ods trace off;
```

- Normality assumption check

```
ods trace on;  
proc univariate data=indata normal plot;  
  var change from baseline;  
  histogram /normal kernel(color=red);  
  ods output TestsForNormality=norm(where=(test="Shapiro-Wilk"));  
run;  
ods trace off;
```

- Wilcoxon Signed Rank Test

```
ods trace on;  
proc univariate data=indata mu0=0 loccount;  
  var change from baseline;  

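### The ECG and laboratory summary tables are limited to combination therapy at nominal visits, leaving monotherapy values, and apparently early-termination values, to listings

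*SAP*

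**What the plan says.** SAP 18.4 states that ECG parameters "will be summarized using the SAF population for the Combination therapy. All ECG data will be listed for both Monotherapy and Combination Therapy". For laboratory data, SAP 18.3 plans "Actual and change from baseline by visit (for quantitative measurements) for Combination Therapy using SAF population", and adds: "A by-patient listing of all laboratory data and pregnancy test data will be presented for both Monotherapy and Combination therapy". Monotherapy ECG and laboratory values therefore appear in listings and in no table.

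SAP 6.3 sets the rule for visit-based tables: "In general, for by-visit summaries, data recorded at the nominal visit will be presented". It excludes unscheduled measurements from those tables, then says: "Listings will include scheduled, unscheduled, retest and early discontinuation data". Appendix 1, however, includes "Early Termination" among the visits to be shown in outputs.

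The protocol schedules ECG and laboratory tests at Visit 1 and Visit 4 only (sections 2.2, 5 and 8.2.3). Its section 10 adds: "Patients who discontinue from the study early will be asked, anyway, to complete all the assessments of Visit 4". The secondary safety objective in section 4 is "To evaluate the safety and tolerability of the monotherapies (NEB 5 mg and AML 5 mg) and of the extemporaneous combinations", and the matching endpoint names ECG and laboratory parameters. Protocol 12.5.6 plans by-visit ECG and laboratory summaries on the Safety population and does not restrict them to combination therapy. SAP 3.3, which records departures from the protocol, does not mention such a restriction.

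**The concern.** For a patient who leaves before Visit 4, the early-termination assessment is the only planned ECG and laboratory result after dosing. If it goes only to a listing, the change tables and the ECG shift table rest on patients who attended a nominal Visit 4. The omission works in one direction, because patients who leave for a cardiac, renal or hepatic finding are more likely than others to have abnormal values. These are risks the protocol itself singles out: it excludes bradycardia, sick sinus syndrome and higher-degree heart block at entry, and sets renal and liver limits for withdrawal.

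The second part is an undeclared narrowing. The protocol promises a safety evaluation of each monotherapy that includes ECG and laboratory parameters, and the SAP provides no summary of either for that phase.

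**Working it through.** **Where each group's values go**

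| Patient group | ECG and laboratory value after dosing | Place in the SAP outputs |
|---|---|---|
| Started combination, attended Visit 4 | Visit 4 | Combination change tables and ECG shift table |
| Started combination, left before Visit 4 | Early termination | Listing under 6.3; possibly a separate row under Appendix 1 |
| Treated in run-in, never started combination | Early termination, on one drug alone | Listing only (18.3, 18.4) |

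Neither test is scheduled at Visit 2, so patients who go on to the combination have no planned value on monotherapy. The third row is therefore the only planned source of ECG and laboratory values after dosing with NEB 5 mg or AML 5 mg alone. A baseline exists for it: both tests are done at Visit 1, and SAP 6.2 names Visit 1 as the laboratory baseline and as the fallback for other safety measurements.

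**How many patients, from the plan's own figures**

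Inputs: 290 screened, about 216 completers, 25% loss (Protocol 5 and 12.2); a cap of 110 per monotherapy group at Visit 2 (Protocol 5, SAP 3.1).

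- Plan's screening figure: 216 / (1 − 0.25) = 288, which agrees with the stated 290 to within rounding.
- Screened but not reaching Visit 4: 290 − 216 = 74, and 74 / 290 = 25.5%.
- Most who can start the combination: 2 × 110 = 220.
- Fewest who do not start it: 290 − 220 = 70. This mixes screen failures with treated run-in withdrawals (BP controlled, intolerant, or outside the adherence range). The split is not given.
- Most who can leave during combination if 216 complete: 220 − 216 = 4, and 4 / 220 = 1.8%.

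As planned, then, the combination gap is small. The larger group is those who leave before the first combination dose, but the number of them with an ECG and laboratory panel after dosing cannot be derived from the documents.

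**The case against.** A reader might infer that the safety tables as a whole describe only patients who tolerated treatment to Week 8. The documents do not support that. The SAF population needs one dose, not completion. Under SAP 18.1 and 18.2, treatment-emergent events, serious events, events leading to discontinuation and deaths are tabulated, with events assigned to the monotherapy or combination phase. SAP 18.5 summarises vital signs, including pulse rate, for both. Protocol 9.9 also makes clinically relevant laboratory abnormalities reportable as adverse events. A patient withdrawn for harm should therefore appear in those tables. They do not, however, show ECG intervals, laboratory changes or interpretation shifts, and section 9.9 has no matching sentence for ECG, although the general definition in 9.1 could capture an ECG finding.

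A reader might also infer a several-fold understatement of clinically significant abnormalities. Neither document gives an abnormality rate, and SAP 18.3 plans no table of laboratory abnormality rates that could be understated. For ECG, suppose purely for illustration that 20% of early leavers and 1% of completers were abnormal. At the 1.8% attrition derived above the overall rate is 0.018 × 0.20 + 0.982 × 0.01 = 1.35%, against 1.0% from Visit 4 alone. A several-fold gap would need much higher attrition than the plan implies, on top of assumed rates.

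Three further objections stand in part. SAP 6.3 is qualified as a general rule and expressly bars only unscheduled measurements; with the Appendix 1 label, and with table templates that are not among the documents, exclusion of early-termination values is the plain reading but not a settled one. Patients may stop treatment and stay in the study, so the Week 8 tables describe Visit 4 attenders, not strictly patients who tolerated the drugs. Finally, the endpoint ties ECG to Visits 1 and 4 and qualifies laboratory parameters as where applicable. Run-in leavers are a selected group, so listing them alone is defensible if the choice is declared. It is not.

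**Conclusion.** The point holds for the ECG and laboratory tables. Two defects remain: SAP 6.3 and Appendix 1 do not agree on whether early-termination values are tabulated, and SAP 18.3 and 18.4 drop the monotherapy summaries that Protocol 12.5.6 leaves in scope, without an entry in SAP 3.3. The second carries more weight.

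The combination effect is at most about 4 of 220 patients, assuming the cap holds and about 216 complete; lower completion would enlarge it. The monotherapy effect falls somewhere within the 70 or more screened patients who do not start the combination, at a number the documents do not fix. It also assumes that patients withdrawn in run-in or at Visit 2 provide the assessments section 10 asks for; that section makes no exception for them. This is a worthwhile correction at low cost, and it does not touch the primary analysis.

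**What to change.** 1. Amend SAP 6.3, 18.3 and 18.4 so that early-termination values are tabulated. Add a row for the last post-dose value (Visit 4 or early termination) to the combination ECG and laboratory change tables, and use that value in the ECG shift table. The denominator is all combination-dosed patients with a post-dose value. This brings 6.3 into line with Appendix 1.
2. Add a descriptive monotherapy summary, by NEB 5 mg and AML 5 mg, of ECG and laboratory values from Visit 1 to early termination for patients who left before the first combination dose. Name Visit 1 as the baseline, and footnote that these patients did not continue and are a selected group. If the summary is omitted, record the departure from Protocol 12.5.6 in SAP 3.3 with the reason.

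The cost is SAP wording and a few table rows. No new visits, tests or data are needed, and no dose or clinical rule changes. The combination abnormality rates may look slightly less favourable, and the monotherapy table will need cautious reading.

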18.5. Vital Signs

The following Vital Signs measurements will be reported for this study:

- Sitting Systolic Blood Pressure (mmHg)
- Sitting Diastolic Blood Pressure (mmHg)
- Pulse Rate (bpm)
- Respiratory Rate (breaths/min)
- Body Temperature (°C)

The following summaries will be provided for vital signs data:

- Actual and change from baseline by visit for Monotherapy and Combination therapy using the SAF population.
- A by-patient listing of all vital signs data will be presented for both Monotherapy and Combination therapy using the SAF population.

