### 6.2.2 Exclusion Criteria

Any patient who meets any of the following criteria will not qualify for entry into the study:

MENARINI	Corp	porate Medical Departme	ent
	Protocol Template		
Identification Number	Version Number	State	Effective date
FORM-000050125	2.0, CURRENT	Effective	08 Jan, 2021

Study Code: MEIN/21/AmNe-Hyp/001

- 1. Significant history of hypersensitivity to nebivolol, amlodipine, other BBs or other dihydropyridines, or any related products (including excipients of the formulations)as outlined in the relevant Investigators Brochures, summary of product characteristics (SmPC) or local package inserts for NEB and AML.
- 2. Patients with serious disorders (in the opinion of the Investigator) which may limit the ability to evaluate the efficacy or safety of the tested medications, including cerebrovascular, cardiovascular, renal, respiratory, hepatic, gastrointestinal, endocrine/or metabolic, hematological, or oncological, neurological, and psychiatric diseases. The same applies for immunocompromised and/or neutropenic patients.
- 3. Patients having a history of the following conditions within the last 6 months: myocardial infarction, unstable angina pectoris, percutaneous coronary intervention, bypass surgery, heart failure, hypertensive encephalopathy, valve replacement (transcatheter aortic valve implantation, mitraclip), cerebrovascular accident (stroke), or transient ischemic attack.
- 4. Patients with condition of hypotension with SBP <90 mmHg and/or DBP <60mmHg.
- 5. Acute heart failure, cardiogenic shock or episodes of heart failure decompensation requiring intravenous inotropic therapy.
- 6. Patients with secondary hypertension of any etiology including renal diseases, pheochromocytoma, Cushing's syndrome, hyperaldosteronism, renovascular disease, thyroid disorders.
- 7. Patients with a narrowing of the aortic or bicuspid valve, an obstruction of cardiac outflow (obstructive, hypertrophic cardiomyopathy), obstruction of the outflow tract of the left ventricle (eg. high grade aortic stenosis) or symptomatic coronary disease.
- 8. Patients with severe renal impairment or renal transplant.
- 9. Patients with clinically relevant hepatic impairment.
- 10. Patients with sick sinus syndrome, including sino-atrial block.
- 11. Patients with second- or third-degree heart block (without a pacemaker).
- 12. Patients with history of bronchospasm and bronchial asthma.
- 13. Patients with untreated pheochromocytoma.

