## 8.2.2 Vital Signs

Vital signs will include body temperature (tympanic measurement), respiratory rate (breaths per minute), sitting BP (see Section 8.1), and pulse rate (beats per minute). All BP measurements will be performed after at least 10 minutes of rest; in sitting position in triplicate (spaced by at least 1 minute), and once in standing position. The mean of the 3 BP readings in sitting position will be recorded on the source documents and in the eCRF. Blood pressure and pulse measurements will be assessed with a completely automated device.

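### The secondary safety endpoint covers clinically significant changes in vital signs and laboratory values, but no planned table counts patients who had one, and standing blood pressure is missing from the SAP

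*SAP*

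**What the plan says.** **Endpoint.** The secondary safety endpoint in Protocol Section 4 (repeated in the synopsis) names, in addition to adverse events, "clinically significant abnormal change in vital signs, electrocardiogram (ECG) (only at Visit 1 and Visit 4" and laboratory parameters. Neither document says what makes a vital sign or laboratory change clinically significant.

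**Vital signs.** SAP 18.5 plans "Actual and change from baseline by visit for Monotherapy and Combination therapy using the SAF population" and a by-patient listing.

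**Laboratory tests.** SAP 18.3 plans "Actual and change from baseline by visit (for quantitative measurements) for Combination Therapy using SAF population" and a listing.

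**Unscheduled values.** SAP 6.3: "Unscheduled measurements will not be included in by-visit summaries". The same section sends unscheduled, retest and early-discontinuation data to the listings.

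**Standing blood pressure.** Protocol 8.2.2 takes readings "in sitting position in triplicate (spaced by at least 1 minute), and once in standing position". It then says: "The mean of the 3 BP readings in sitting position will be recorded on the source documents and in the eCRF". It does not say where the standing reading is recorded. The blood pressure parameters in SAP 18.5 are the sitting systolic and diastolic values only.

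**The concern.** All patients in the assessment period take a beta-blocker with a calcium channel blocker, and those uncontrolled at Visit 3 are uptitrated. The safety question is how many patients became hypotensive, bradycardic or symptomatic on standing, or developed abnormal liver or renal values. A by-visit distribution does not answer it, because a few marked falls barely move the centre. The report could truthfully describe unremarkable average changes while the patients who matter are visible only to someone reading the listings.

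Unscheduled values make this worse for laboratory tests and ECG. The flow chart schedules both at Visit 1 and Visit 4 only, so there is one planned on-treatment time point. Protocol 8.2.4 allows extra ECGs when clinically indicated. A value obtained because of a suspected problem would be listed and not summarised.

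**Working it through.** There is no stated figure to reproduce, so the main check sets the two documents side by side.

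| Domain | Endpoint (Protocol 4) | Analysis in Protocol 12.5.6 | Analysis in SAP | Patients counted? |
|---|---|---|---|---|
| ECG | yes | values, change, shift table | 18.4: the same, with a clinically significant category | yes, scheduled visits |
| Physical examination | not named in the endpoint | shift table | 18.6: shift table | yes |
| Vital signs | yes | values and change | 18.5: values and change, listing | no |
| Laboratory | yes | values and change | 18.3: values and change, listing | no |
| Standing BP | required by 8.2.2 | not mentioned | not listed in 18.5 | no |

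**Other routes into a table**

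1. *Adverse events.* Protocol 9.9 has a specific rule: laboratory abnormalities that the investigator considers clinically relevant are reported as adverse events. SAP 18.1 then counts treatment-emergent events. Vital signs have no such rule, only the general definition in Protocol 9.1. Whether a low pulse or pressure is counted is left to each investigator, at approximately 25 sites, without a common criterion.
2. *Withdrawal.* The liver and renal limits in Protocol 8.2.3 lead to withdrawal, and SAP 9.1 tabulates withdrawals. This catches only patients who leave.
3. *Descriptive statistics.* SAP Section 7 gives n, mean, SD, median, minimum and maximum. The minimum shows the lowest scheduled value, not the number of patients near it.

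**How little a distribution summary reveals (all rates and distributions assumed; 216 is the planned number of completers)**

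*Mean shift* = share affected × size of extra fall. With 2% of patients falling an extra 20 mmHg: 0.02 × 20 = 0.4 mmHg. The count would be about 4 of 216 = 1.9% (Clopper-Pearson 95% CI 0.5% to 4.7%). With 5%: 0.05 × 20 = 1.0 mmHg against 11 of 216 = 5.1% (2.6% to 8.9%). A count of zero is informative too: its upper 95% limit is 1.7%.

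*Pulse below 50 bpm at Visit 4.* Assume a normal distribution and whole-number readings, so the cut is at 49.5. The share is Φ((49.5 − mean)/SD).

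| Mean, SD | z | Share | Of 216 |
|---|---|---|---|
| 68, 8 | −2.31 | 1.0% | 2 |
| 68, 10 | −1.85 | 3.2% | 7 |
| 64, 8 | −1.81 | 3.5% | 8 |
| 64, 10 | −1.45 | 7.4% | 16 |

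The range is 1.0% to 7.4%. Means anywhere in 64 to 68 bpm look unremarkable, yet the number affected varies about sevenfold.

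**The case against.** The strongest reply is that the plan is less bare than it looks. Clinically relevant laboratory abnormalities must be reported as adverse events and so reach the event tables. ECG and physical examination have shift tables, and ECG heart rate is summarised. The summaries give the spread and extremes, and the listings hold every value, including unscheduled ones. The SAP follows Protocol 12.5.6 and drops no count that the protocol had planned. SAP Section 8 refers to table templates that are not among the documents, so an abnormality table could exist there. Early leavers are asked to complete the Visit 4 assessments (Protocol 10), and Early Termination is a named output visit (SAP Appendix 1).

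All of this is accurate, and it rules out the stronger readings. A reader might infer that clinically significant changes are never counted, or that the safety data are reduced to mean changes. The documents support neither. A reader might also infer that standing readings are discarded, but Protocol 8.2.2 is silent on their capture and does not exclude it. Nor do the numeric limits define the endpoint. "Patients with condition of hypotension with SBP <90 mmHg and/or DBP <60mmHg" is an exclusion criterion, as is the heart-rate limit, and the liver and renal values are withdrawal criteria.

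The narrower point remains. The endpoint lists abnormal changes separately from adverse events, so event counts do not deliver it, least of all for vital signs. That the gap begins in Protocol 12.5.6 means the protocol disagrees with its own endpoint. Unseen templates do not replace a rule in the text for what counts as abnormal.

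**Conclusion.** The point holds in this limited form. For vital signs and laboratory tests, a stated secondary endpoint has no matching analysis in the text of either document. Patients with clinically significant changes are tabulated only through adverse event reporting or withdrawal, and unscheduled values only reach listings. Standing blood pressure is required but has no stated path to the report, and the list of departures from the protocol in SAP 3.3 does not mention this.

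The size cannot be taken from the documents. On the assumed pulse distributions, roughly 2 to 16 of 216 patients could be below 50 bpm without the table showing how many. The safety population also includes patients treated only in the run-in, so its denominator may be larger than 216. The conclusion does not rest on these figures, and it does not affect the primary efficacy analysis.

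**What to change.** 1. **Patient counts.** Add to SAP 18.3 and 18.5 a table, by treatment phase, of patients with at least one on-treatment abnormal value, including unscheduled and early-termination values. Use limits already printed in the protocol: SBP below 90 or DBP below 60 mmHg and the heart-rate limits (6.2.2); ALT or AST above 2.5 × ULN, total bilirubin above 1.5 × ULN and creatinine clearance below 30 mL/min (8.2.3). Label them as reporting cut-offs only, neither the clinical definition of the endpoint nor a management rule. State how creatinine clearance is obtained, since the laboratory list in 8.2.3 gives creatinine and eGFR.
2. **Worst-value shifts.** Add shifts from baseline to worst post-baseline value for laboratory tests and ECG, with unscheduled values included.
3. **Standing blood pressure.** Report standing SBP and DBP and the sitting-to-standing difference where captured or recoverable from source. Otherwise record the omission in SAP 3.3.
4. **Laboratory.** Reconcile the local laboratory in Protocol 8.2.3 with the central laboratory in SAP 18.3. Counts relative to the ULN depend on which reference ranges apply.

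The cost is two or three extra tables, mostly from data already collected. Standing readings are the exception. The SAP is dated 11 November 2022 and the protocol planned the last patient out for early December 2022, so capturing them may mean retrospective entry from source.
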